1.1. Disease

It has been estimated that carotid artery disease accounts for 20-30% of the greater than 500,000 new strokes that occur annually in the United States¹. As stroke is the leading cause of serious, long-term disability in the United States, treatment of carotid artery disease may diminish part of the \$53.6 billion yearly health care costs associated with the treatment of stroke².

1.2. Historical Treatments

Treatment options for carotid artery disease include the current standard of care, carotid endarterectomy (CEA), medical therapy, and the continuously evolving procedure of carotid artery stenting (CAS).

CEA remains the gold standard as an effective technique for the treatment of chronic carotid artery stenosis associated with stroke. The technique is endorsed by the American Heart Association (AHA) as a first-line therapy for symptomatic subjects with recent cerebral ischemia and carotid artery diameter stenosis exceeding 70% and for carotid stenosis exceeding 60% in asymptomatic subjects with surgical risk less than 3% and a life expectancy of at least 5 years^{1,3}. However, for CEA to provide a greater benefit than medical therapy, the combined morbidity and mortality rate should be under 3% for asymptomatic subjects and less than 6% for symptomatic subjects⁴.

In patients at high risk for complications during CEA, such as those with anatomic or physiologic co-morbidities, outcomes with surgery are less well defined and in some cases documented to be worse than the standard surgical risk patient⁵. In these cases CAS has been shown to be a potentially safer and equally effective stroke reduction therapy⁶. Furthermore, high surgical risk registry data have demonstrated a continued reduction in stroke/MI/death rates over the last several years suggesting that as technique, patient selection, and technology improves, so do outcomes^{7,8}. In the standard risk patient, the recently released results of the Carotid Revascularization Endarterectomy vs. Stent Trial (CREST) study found equivalence between the two strategies in terms of the primary endpoint of death, stroke, and myocardial infarction to 30 days plus ipsilateral stroke to 4 years⁹.

Advantages and Disadvantages with Current Carotid Stents

Closed Cell vs Open Cell

Currently, the stents available for CAS are divided into two types; Closed-Cell and Open-Cell. Locally approved Closed-Cell stents, such as the Xact® Carotid Stent System (Abbott Vascular, Santa Clara, CA) or the Wallstent® Monorail® System (Boston Scientific Corporation Natick, MA) are characterized by individual apices of the stent frame being connected by a strut to the apices in the adjacent row and is further characterized by each of the individual apices having a smaller cell size. The obvious benefit from such a design is that the stent provides a higher degree of plaque stabilization, thus minimizing plaque protrusion through the stent struts and maintaining greater contact with the vessel wall. However, such a design is typically considered to be more rigid and not able to conform to the native anatomy with clinical reports of kinks forming in the vasculature at the distal end of the device¹⁰.

GORE CONFIDENTIAL INFORMATION

In contrast, Open Cell stents, such as the PRECISE® Carotid Stent System (Cordis, Miami, FL), are characterized as having fewer connections between adjacent apices and thus having larger cell sizes. The benefit of such a design allows for a higher degree of flexibility, which conforms to the native anatomy, however the design has less of a scaffolding effect and does not cover the plaque as efficiently as do Closed Cell stents. An additional issue reported is the so called "fish-scaling" of the stent struts where when deployed in tortuous anatomy, the stent struts come out of alignment and appear as individual scales protruding from the stent¹¹.

As carotid artery stenting devices and techniques continue to evolve, many clinicians have described the optimal design. Consistent with these statements from the podium at scientific presentations, Stefan Müller-Hülsbeck describes the ideal carotid stent as having features which include *"scaffolding that is adequate enough to control plaque prolapse but has acceptable levels of flexibility, conformability, and radial strength to track to the lesion, appose the vessel wall, and control recoil"*.¹²

1.3. Study Device Description

GORE® Carotid Stent System

The GORE® Carotid Stent is designed as a true "hybrid" stent in that it incorporates the flexibility and conformability of an Open Cell stent as well as the plaque stabilization of the Closed Cell Stent. Additionally, the device is coated with a covalently bonded Carmeda® Bioactive surface heparin to create an anti-thrombogenic surface. Ease of use of the system is designed into the delivery system which not only offers a single-handed deployment handle, but allows complete closure of the hemostatic valve to aid in stabilization of the delivery system and minimized blood loss.

The GORE® Carotid Stent System consists of a self expanding nitinol stent frame with a 500 μ pore size lattice on the exterior of the stent frame. Additionally the stent frame and lattice are coated with a permanently bound anti-thrombogenic surface in the form of CBAS® Heparin. The stent is mounted on a 5Fr or 6Fr introducer sheath compatible delivery system with a working length of 135 cm and a single-handed delivery handle.

The GORE® Carotid Stent, used with the GORE® Embolic Filter, is indicated for the treatment of carotid artery stenosis in patients deemed at high surgical risk for CEA.

- Patients with symptomatic carotid artery stenosis, ≥50%, as confirmed by ultrasound or angiography.
- Patients with asymptomatic carotid artery stenosis, ≥80%, as confirmed by ultrasound or angiography.
- Patients must have a Reference Vessel Diameter of 3.7 mm 9.0 mm.

GORE® Carotid Stent MD134865 GCS 10-08 PROT Revision#: 3 Doc Type: SP

CONFIDENTIAL INFORMATION MD133246 Protocol Template Revision#: 1 Doc Type: GC

1.4. Gore Embolic Protection System

GORE® Embolic Filter

The GORE® Embolic Filter consists of a device, a delivery catheter, and a retrieval catheter, and is compatible with guiding catheters and sheaths having a minimum inner diameter of 0.066". The GORE® Embolic Filter is indicated for general use as a guide wire and embolic protection system during angioplasty and stenting procedures in carotid arteries with reference vessel diameters of 2.5 to 5.5mm.

2. Study Objectives

2.1. Primary Objective(s)

The primary objective of this study is to evaluate the safety and efficacy of the GORE[®] Carotid Stent for the treatment of carotid artery stenosis in patients at increased risk for adverse events from carotid endarterectomy.

3. Study Design

3.1. Description of Study Design

This study is a prospective, multicenter, multinational, single-arm clinical study to evaluate the safety and efficacy of the GORE® Carotid Stent for the treatment of carotid artery stenosis in patients at increased risk for adverse events from carotid endarterectomy. The primary endpoint is a composite of Major Adverse Events through 1 year post-index procedure and will be compared to a performance goal developed from published carotid endarterectomy outcomes in a high-risk population.

A maximum of 50 investigative sites in the U.S will participate in this study. Three hundred twelve (312) subjects will be enrolled in this study with a limit of 40 subjects enrolled per site. The anticipated accrual rate is approximately 15-20 subjects per month for a total accrual period of approximately 18-24 months.

Patients may be enrolled into the clinical study provided all inclusion and no exclusion criteria are met. Subjects will be evaluated through hospital discharge and return for follow-up visits at 30 days, 6 months, and 1, 2, and 3 years post-procedure.

The total study duration from start-up to close-out is expected to be 60 months. A primary endpoint analysis will be submitted to the FDA for PMA approval upon completion of the 1-year follow-up.

3.2. Study Endpoints

3.2.1. Definitions

Stroke: An acute neurologic event with focal symptoms and signs, lasting for 24 hours or more.

Minor Stroke: A stroke that resolves completely within 7 days or increases the NIHSS by < 4 points.

Major Stroke: A stroke that persists after 7 days and increases the NIHSS by \geq 4 points.

Ipsilateral Stroke: A stroke affecting the cerebral hemisphere supplied by the carotid artery that is being treated.

Myocardial Infarction: A troponin level that is twice the upper limit of the normal range or higher according to the center's laboratory, accompanied by either chest pain/symptoms consistent with ischemia or ECG evidence of ischemia.

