3.2.2. Primary Endpoint

The primary study endpoint is a composite of Major Adverse Events (MAE) defined as death, any stroke, or myocardial infarction (MI) through 30 days post-index procedure, and ipsilateral stroke between 31 days and 1 year. All primary endpoint events will be adjudicated and determined by the study Clinical Events Committee.

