4.2. Inclusion Criteria

For inclusion in the study, a patient must meet all general inclusion criteria, as shown below: **General Inclusion Criteria:**

- 1. Patient is at least 18 years old at informed consent
- 2. Patient is willing and capable of complying with all study protocol requirements, including specified follow-up period and can be contacted by telephone.
- 3. Patient is willing to provide written informed consent prior to enrollment in study.
- 4. Patient has no childbearing potential, or is a non-lactating female of childbearing potential practicing an acceptable method of birth control with a negative pregnancy test within 10 days of study procedure.
- 5. Patient is either:
 - Symptomatic with carotid stenosis ≥50% as determined by angiography using NASCET methodology¹³. Symptomatic is defined as amaurosis fugax ipsilateral to the carotid lesion; TIA or non-disabling stroke within 180 days of the procedure within the hemisphere supplied by the target vessel; or
 - Asymptomatic with carotid stenosis ≥80% as determined by angiography using NASCET methodology.
- 6. Patient has a target lesion located at the carotid bifurcation and/or proximal ICA.
- 7. Patient has a single de novo or restenotic (post CEA) target lesion that can be covered by a single 40mm stent.
- 8. Patient has a stent landing zone diameter between 3.7 mm and 9.0 mm

High Risk Inclusion Criteria:

For inclusion in the study, a patient must qualify in **at least one** High-Risk condition, as shown below:

Anatomic Conditions

- 1. Patient has surgically inaccessible lesions at or above the level of C2 or below the clavicle.
- 2. Patient is status/post radical head or neck surgery or radiation therapy.
- 3. Patient has spinal immobility of the neck.
- 4. Patient has the presence of tracheostomy stoma.
- 5. Patient has laryngeal palsy or laryngectomy.
- 6. Patient has contralateral laryngeal nerve paralysis.
- 7. Patient has restenosis after a previous CEA.

Co-morbid Conditions

[figure not shown]
- 1. Patient is \geq 75 years of age at time of enrollment.
- 2. Patient has NYHA Class III or IV congestive heart failure (CHF).
- 3. Patient has chronic obstructive pulmonary disease (COPD) with FEV <30%.
- 4. Patient has a left ventricular ejection fraction (LVEF) <30%.
- 5. Patient has documented uncontrolled diabetes.
- 6. Patient has unstable angina with ECG changes.
- 7. Patient has had a recent myocardial infarction (≥72 hours, <30 days).

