9.4. Clinical Events Committee

An independent Clinical Events Committee (CEC) will review potential primary endpoint events and adjudicate events based on endpoint definitions in the study protocol. The CEC will be comprised of an interdisciplinary team with pertinent knowledge in carotid stenting or the cardiovascular and/or nervous system who are not directly involved in the conduct of the study. The members will be compensated for their involvement in the CEC, including reimbursement for reasonable travel expenses to attend meetings.

This committee will operate under pre-specified procedures as outlined in the CEC Charter. The adjudication process will be initiated after a potential primary endpoint event is reported by the site.

10. Statistical Analysis

[figure not shown]

[figure not shown]
CONFIDENTIAL INFORMATION MD133246 Protocol Template Revision#: 1 Doc Type: GC

GORE® Carotid Stent MD134865 GCS 10-08 PROT Revision#: 3 Doc Type: SP

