#### 2.5 Study Endpoints

#### 2.5.1 Primary Endpoint

The primary study endpoint is a composite of Major Adverse Events (MAE) defined as death, any stroke, or myocardial infarction (MI) through 30 days post-index procedure, and ipsilateral stroke between 31 days and 1 year (365 days). All primary endpoint events will be adjudicated and determined by the study Clinical Events Committee (CEC).

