#### 4.3 **Primary Endpoint**

The primary endpoint of 1-year MAE will be calculated as a subject-based binomial proportion. The numerator will be the count of subjects who experience death, any stroke, or MI through 30 days post-index procedure, or ipsilateral stroke through one year (365 days) post-index procedure. The denominator will be the count of subjects free of MAE and with clinical follow-up of at least 335 days post-index procedure, plus the count of subjects in the numerator. Only MAE adjudicated by the CEC will be used in this analysis. Acceptable clinical follow-up includes the Subject Evaluation CRF, duplex ultrasound, modified Rankin scale, and NIHSS.

A one-sided 95.1% upper confidence bound will be calculated (using the standard error based on  $H_0$ ) and compared to the prespecified performance goal. If this bound is less than the performance goal, then the primary endpoint is met and the test device will have demonstrated acceptable performance. The *P* value for the corresponding one-sided normal

approximation to the binomial test will be reported. The primary hypothesis test will use  $\alpha$ =0.049 to ensure an overall Type-1 error rate  $\leq$ 0.05.

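### The stroke definition requires 24 hours of symptoms and has no clause for earlier death, so, read literally, a rapidly fatal ipsilateral stroke after day 30 is not an MAE

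*Protocol*

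**What the plan says.** Protocol 3.2.1 defines stroke as "An acute neurologic event with focal symptoms and signs, lasting for 24 hours or more". Ipsilateral stroke is "A stroke affecting the cerebral hemisphere supplied by the carotid artery that is being treated", so it must first be a stroke and it inherits the 24-hour test.

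The same section grades severity. A minor stroke resolves fully within 7 days or raises the NIHSS by less than 4. A major stroke is still present after 7 days and raises the NIHSS by 4 or more.

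The composite in Protocol 3.2.2 is death, any stroke or "myocardial infarction (MI) through 30 days post-index procedure, and ipsilateral stroke between 31 days and 1 year". SAP 2.5.1 has the same components and puts 1 year at 365 days.

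Protocol 9.4 has the CEC "adjudicate events based on endpoint definitions in the study protocol", and starts adjudication when a site reports a potential primary endpoint event. SAP 4.3 adds "Only MAE adjudicated by the CEC will be used in this analysis". On evaluability, SAP 4.3 says "The denominator will be the count of subjects free of MAE and with clinical follow-up of at least 335 days post-index procedure", plus the subjects who had an MAE. SAP 4.10 requires a worst-case analysis in which nonevaluable subjects are counted as failures.

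**The concern.** After day 30 the composite rests on one event type, ipsilateral stroke. The duration test separates stroke from transient attacks, but without a death clause it also removes the strokes that end in death before 24 hours. These are the most severe form of the event that the late component is meant to capture.

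The primary test compares one arm with a fixed performance goal, so no concurrent control group shares the omission. Within the trial, leaving such an event out can only lower the observed MAE rate.

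**Working it through.** **Step 1. What can be reproduced.** The point concerns wording and depends on no stated result. The performance goal, expected rate and power cannot be read in the public documents. The one related figure that can be checked is alpha: 1 − 0.951 = 0.049, which agrees with Protocol 10.4.5 and SAP 4.3. The matching normal quantile is z = 1.6546.

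**Step 2. Apply the rules to a treated-side stroke that kills 10 hours after onset (an illustrative case).**

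| Time of event | Stroke under 3.2.1? | Death a component? | Place in the primary analysis |
|---|---|---|---|
| Through day 30 | No (10 h < 24 h) | Yes | MAE, through the death |
| Day 31 to 334 | No | No | Not an MAE; under 335 days of follow-up, so outside the denominator |
| Day 335 to 365 | No | No | Not an MAE; counted as MAE-free if at least 335 days of clinical follow-up are on record |

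In the middle row the SAP 4.10 worst-case analysis counts the subject as a failure. In the last row it does not if the subject is evaluable.

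**Step 3. Apply the severity split.** Take a stroke with an NIHSS rise of 4 or more and death on day 3 after onset. It did not resolve and the rise is not below 4, so it is not minor. It did not persist beyond 7 days, so it is not major. This leaves severity reporting incomplete, but it does not change the primary endpoint, which does not use severity.

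**Step 4. Size of one event.** A subject outside the denominator enters both numerator and denominator when counted, so the shift is (x + 1)/(n + 1) − x/n. Assume a base rate of about 9%:

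- n = 312, x = 28: 29/313 − 28/312 = 9.27% − 8.97% = 0.29 points (from unrounded values).
- n = 260, x = 23: 24/261 − 23/260 = 9.20% − 8.85% = 0.35 points.

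A subject otherwise scored MAE-free (last row of the table) shifts the rate by 1/n: 0.32 points at n = 312 and 0.38 points at n = 260.

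**Step 5. How many events.** The documents give no frequency. Assume that 1–3% of 312 subjects (about 3 to 9) have a late ipsilateral stroke, and that 5–10% of those strokes are fatal within 24 hours. The expected number is 3 × 0.05 = 0.15 to 9 × 0.10 = 0.9.

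**Step 6. Context for the test.** With the standard error under H₀, the trial passes if x < n·PG − 1.6546·√(n·PG·(1 − PG)), where PG is the performance goal. For n = 300 evaluable subjects (assumed):

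| Assumed PG | Right-hand side | Most events that pass |
|---|---|---|
| 10% | 21.40 | 21 |
| 12% | 26.69 | 26 |
| 14% | 32.06 | 32 |
| 16% | 37.49 | 37 |

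At n = 301 the right-hand sides are 21.49, 26.79, 32.18 and 37.64, so the limits do not move. Counting one such subject changes the conclusion only if the observed count already stands exactly at the limit.

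**The case against.** The best reply is that adjudication will resolve this. Protocol 3.2.2 leaves primary endpoint events to the CEC, Protocol 9.1.4 has death certificates and autopsy reports obtained for it, and a deficit present until death can sensibly be read as one that never resolved. The CEC Charter, which is not among the documents, may say so. This shows that events need not be lost in practice. It does not remove the gap: the CEC is tied to the protocol definitions, and a site that reads the 24-hour test literally may not report the case as a potential endpoint. A primary endpoint should not admit two readings.

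A second reply is that the worst-case analysis counts the subject who dies before day 335 as a failure. That stands, and such a death is not hidden. But that analysis treats all nonevaluable subjects alike, and it does not repair the primary test.

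A reader might also infer that confining ipsilateral stroke to the cerebral hemisphere is an error, because an ipsilateral retinal infarction is then left out although the eye counts at entry: "Symptomatic is defined as amaurosis fugax ipsilateral to the carotid lesion". The documents do not support this. Inclusion criterion 5 lists amaurosis fugax separately from hemispheric events. It also lists TIA, which is not an endpoint event either. Entry symptoms and endpoint events were therefore not meant to match, and the hemispheric limit is a defensible prespecified choice. Retinal events would still be reported and tabulated as adverse events.

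**Conclusion.** The gap is real on the text. As written, an ipsilateral stroke after day 30 that is fatal within 24 hours is not an MAE, and the subject usually leaves the primary denominator. The severity grading also has no place for a stroke with an NIHSS rise of 4 or more that is fatal before day 7.

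The likely size is 0 to 1 events, each worth about 0.3 percentage points. The frequency, the 9% base rate and the illustrative goals are all assumptions.

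A reader might infer that the trial is biased in favour of the device. The documents do not establish that. The omission lowers the trial's own rate, but the comparison is with a goal taken from published endarterectomy outcomes whose event definitions cannot be seen here. If those sources left out early fatal strokes in the same way, trial and goal match. If they counted them, the omission favours the device. The case for the change is that it is cheap and makes the primary endpoint unambiguous, not that it is likely to alter the result.

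**What to change.** 1. In Protocol 3.2.1, extend the duration test so that it reads: lasting for 24 hours or more, or resulting in death before 24 hours.
2. In the same section, state that a fatal stroke is classed as major, whenever death occurs.
3. In Protocol 9.4 and the CEC Charter, have sites refer every death between day 31 and day 365 with a possible neurological cause, and have the CEC classify each one as ipsilateral stroke or not. The referral instruction is needed because adjudication now starts only from a site-reported potential endpoint event.
4. Check how the goal's source studies counted early fatal strokes, and report that with the result.

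Leave the hemispheric limit on ipsilateral stroke as it is.

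The cost is a short amendment, a few more deaths to adjudicate (including a second look at any late deaths already reviewed) and possibly a slightly less favourable MAE rate. Death records are already to be obtained for the CEC under Protocol 9.1.4, so little new data collection is needed.

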3.2.2. Primary Endpoint

The primary study endpoint is a composite of Major Adverse Events (MAE) defined as death, any stroke, or myocardial infarction (MI) through 30 days post-index procedure, and ipsilateral stroke between 31 days and 1 year. All primary endpoint events will be adjudicated and determined by the study Clinical Events Committee.

3.2.3. Secondary Endpoints

Stent Technical Success: Successful deployment of a GORE® Carotid Stent

EPD Technical Success: Technical success for the GORE® Embolic Filter is defined as: Device delivered, placed, and retrieved without requiring assisting interventional methods.

Procedure Success: Successful GORE® Carotid Stent deployment, <30% residual angiographic stenosis by visual assessment post-procedure in the target lesion and no in-hospital (pre-discharge) Major Adverse Event

30-Day Major Adverse Events: Composite of death, any stroke, or myocardial infarction through 30 days post-index procedure

In-stent Restenosis: Measured as percent stenosis at follow-up evaluation within the stented lesion or within 5 mm proximal or distal to the stent. Additionally will assess percent of subjects with stenosis \geq 50% by ultrasound and \geq 80% by angiographic evaluation

Target Lesion Revascularization (TLR): any clinically driven revascularization procedure of the original treatment site, including angioplasty, stenting, endarterectomy, or thrombolysis, performed to open or increase the luminal diameter inside or within 5 mm of the previously treated lesion.

4. Study Population

